Demographic information was collected at the baseline interview. We collected data on age, sex/gender, race and ethnicity, primary language, and education level. The covariates/confounders assessed in our model include age, sex/gender, and education, chosen based on the conceptual model exploring the relationship between health literacy and various health outcomes.⁴⁹ We will report descriptive statistics of demographic variables. To ease interpretation, **Education** will be treated as a dichotomous variable with two categories: high school/GED level education or less versus more than high school education. **Gender** will be treated as dichotomous variable (male/female), because no participants identified as transgender or non-binary in this sample (although our assessment procedures were designed to accommodate non-binary participants). **Age** (in years) will be treated as continuous variable.

Primary Covariate

We will focus on race and ethnicity as primary covariate in our mediation analysis exploring the relationship between race/ethnic status and vaccine confidence. **Race/ethnicity status** will be dummy coded in the following way using white (non-Hispanic) as the reference category:

- X1 =1 if Black/African American (Non-Hispanic); X1=0 otherwise
- X2 = 1 if Latin X/Hispanic Ethnicity; X2=0 otherwise
- X3 = 1 if Other Race/Ethnicity (Non-white); X3 =0 otherwise

The other race category will include participants of mixed race and individuals who identified as Asian, Pacific Islander, or American Indian, categories with fewer participants.

Health literacy: Hypothesized Mediator

Health literacy was measured at baseline using Health Literacy Assessment Using Talking Touchscreen Technology (Health LiTT),⁵⁰ a computerized assessment that does not require an interviewer. This measure has been validated in English and Spanish. We will define **Health Literacy** as a continuous T score obtained from Health LiTT where a higher score is associated with greater degree of health literacy.

Vaccine Confidence Index: Outcome

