2. Determine whether health literacy mediates the relationship between baseline demographics (e.g., education, age, gender) and future stress-related symptoms using the PCL-5. Will run separate models for English and Spanish.
3. Determine which aspects of health-related quality of life (measured by PROMIS-57 Profile v2.1, which includes Physical Function, Anxiety, Depression, Fatigue, Sleep Disturbance, Ability to Participate in Social Roles and Activities, Pain interference, and Pain Intensity) are associated with trauma symptoms measured by the PCL-5, after statistically controlling for demographics and health literacy.

Hypotheses:

1. There will be a significant association between health literacy (measured by Health LiTT) and the PCL-5 scale, such that lower health literacy will be associated with higher trauma-related symptoms.
2. Health literacy serves as a mediator between baseline demographics (education, age, gender, ethnicity) and future stress related symptoms as per the PCL-5.
3. Higher levels of self-reported anxiety, depression, and ability to participate in social roles and activities from the PROMIS-57 will be associated with higher PCL scores.

Data Description

Datasets used

NIH-funded Reducing Assessment Barriers for Patients with Low Health Literacy dataset, also known as the DIF study (PI: [name]). All timepoints will be analyzed for this project (baseline, 3-month, and 6-month time points). The dataset is not publicly available. The data are not public, but will be made available to us from the DIF team at the time of publication.

Data Collection Procedures (from parent study)

Participants included those who were aged 18 or older, could provide informed consent, were open to randomization for mode of administration, were willing to complete questionnaires, fluent in English and/or Spanish, willing to attend three face-to-face sessions, and did not have plans to move outside of the study area for six months. Study participants were recruited from two sites: Northwestern University (Chicago, IL) and Boston Medical Center (Boston, MA). Participants were ineligible for the study if they had significant cognitive

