# The model will have a form similar to the R code below:  
# Note: race and ethnicity will be analyzed in English-speaking participants  
model <- lm(posttraumatic_stress ~ Health_LiTT + education + age + gender + race, data = data)  
summary(model)
```

The results will be evaluated by examining the magnitude and 95% confidence intervals for health literacy, as measured by Health LiTT. We will use “non-Hispanic white” as the reference category, and all other categories will be binary coded (0/1).

For Aim 1, the statistical analysis will involve a multiple linear regression model to explore how various factors such as health literacy (as measured by the Health LiTT test) and demographics such as education, age, gender, race, and ethnicity predict levels of posttraumatic stress (as per the PCL-5). The linear regression model will estimate the relationships between these variables. This will also include the calculation of coefficient estimates, confidence intervals, and significance levels. We will also explore assumptions of linear regression such as linearity, homoscedasticity, normality of residuals, and multicollinearity. We will assess all these aspects to ensure that there is no individual data point that disproportionately impacts results. For ethnicity, “non-Hispanic white” will serve as the reference group, and other ethnic categories will be binary coded (0/1; 0 for not belonging to this category and 1 for belonging to it). The results will be evaluated by examining the magnitude and 95% confidence intervals for health literacy, as measured by Health LiTT. We will also evaluate model goodness-of-fit (via R-squared statistic) to understand more about how well the model explains any variability in posttraumatic stress. We may explore interaction terms and model comparison as needed.

Aim 2 example code:

```

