For Aim 3, we will conduct analysis that aims to identify which aspects of health-related quality of life (as measured by the PROMIS-57 Profile v2.1) are associated with posttraumatic stress-related symptoms (as measured by the PCL-5). The PROMIS-57 includes domains such as Physical Function, Anxiety, Depression, Fatigue, Sleep Disturbance, Ability to Participate in Social Roles and Activities, Pain interference, and Pain Intensity. We will examine the relationship between these quality-of-life domains and trauma symptoms while statistically controlling for demographic variables and health literacy. For this analysis, we will begin with assessing the correlations (using the psych package in R) between the PROMIS-57 domains and PCL-5, in the overall sample and also stratified by language. This may identify any significant relationships between quality of life domains and posttraumatic stress symptoms. Domains that suggest association with posttraumatic stress symptoms will be entered into a regression model with demographics included as covariates (to control for potential influence) and further evaluate the distinctive influence of quality of life domains predicting trauma symptoms. Lastly, language will be used as a moderator in the regression model to assess whether these relationships differ by language.

Effect size

I am focusing on unstandardized regression coefficients. In some cases, I may inspect standardized regression coefficients.

Inference criteria

Any regression coefficients with a 95% CI not containing zero will be regarded as significant.

Assumption Violation/ Model Non-Convergence

We will inspect the distribution of residuals for each model. If residuals suggest a departure from normality, robust regression and/or bootstrapping will be considered. If a model does not converge, we will explore other estimators in lavaan or modifications to the model, such as dropping covariates that are not needed.

Exploratory analysis

For research questions 1 and 3, language will be explored as a moderator. For research question 2, we will explore separate models for English and Spanish.

REFERENCES CITED

1. Affairs HlrotCoS. Ad Hoc Committee on Health Literacy for the Council on Scientific Affairs, American Medical Association. *JAMA*. 1999;281(6):552-7.

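### The PCL-5 project is to use all three visits, but Aims 1 and 3 specify only lm() with no visit or participant term; if visits are stacked, the Aim 1 Health LiTT interval is too narrow

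*SAP*

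**What the plan says.** The section is the SAP's project on health literacy as a possible mediator of stress and trauma symptoms (PCL-5), added for Version 5.1.

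- **Data.** Under Datasets used: "All timepoints will be analyzed for this project (baseline, 3-month, and 6-month time points". The sentence covers the whole project and is not tied to one aim.
- **Aim 1 model.** The example code is "lm(posttraumatic_stress ~ Health_LiTT + education + age + gender + race, data = data", introduced by "The model will have a form similar to the R code below". The prose below it also describes a multiple linear regression. Neither names a visit.
- **Aim 3 model.** It relies on lm() and correlations, again with no visit named.
- **Aim 2.** The outcome is future PCL-5, but the visit that supplies it is not named.
- **Checks.** "We will also explore assumptions of linear regression such as linearity, homoscedasticity, normality of residuals, and multicollinearity". Independence of observations is not on the list.
- **Fallback.** "If residuals suggest a departure from normality, robust regression and/or bootstrapping will be considered". A separate provision covers models that do not converge. Neither responds to repeated measures.
- **Decision rule.** "Any regression coefficients with a 95% CI not containing zero will be regarded as significant".

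Two facts come from elsewhere. The PTSD Checklist is scheduled at all three visits (SAP Table 1; protocol section 4.3). Health LiTT is scheduled at Visit 1 only, and the SAP's vaccine addendum confirms this: "Health literacy was measured at baseline using Health Literacy Assessment Using Talking Touchscreen Technology".

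**The concern.** Ordinary regression treats every row as an independent observation. If the Aim 1 data frame holds one row per person per visit, a participant with three visits supplies three correlated PCL-5 scores against one unchanging Health LiTT score. The extra rows add little information about the Health LiTT coefficient, but lm() counts them as new participants. The point estimate is not the problem; its standard error is.

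Significance in this project rests on whether the 95% interval excludes zero. An interval that is too narrow therefore turns directly into false positives for the main Aim 1 result. Nothing in the listed checks would bring the error to light.

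**Working it through.** **Inputs**

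- Visits: 3 (SAP, Datasets used).
- Health LiTT: constant within person (SAP Table 1; vaccine addendum).
- Two-sided 5% level through the 95% interval (SAP, Inference criteria).
- Within-person residual correlation of PCL-5, rho: not given in either document. Assumed, mainly .5 to .8.
- Completeness: not given for PCL-5. The SAP's Study Objectives put the parent sample at 728 and say that some participants lack later questionnaires. No N is given for the PCL-5 project; the formula below does not need one.

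The section states no power, SD or correlation, so there is no figure of its own to reproduce.

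**Formulas**, for a covariate constant within person and m visits per person:

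- DEFF = 1 + (m − 1) × rho, the true variance divided by the variance lm() reports
- naive/true interval width = 1/√DEFF
- type I error = 2 × [1 − Φ(1.96/√DEFF)]

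**Three complete visits, stacked**

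| rho | DEFF | naive/true width | too narrow by | type I error |
|---|---|---|---|---|
| .3 | 1.6 | 0.791 | 20.9% | 12.1% |
| .5 | 2.0 | 0.707 | 29.3% | 16.6% |
| .6 | 2.2 | 0.674 | 32.6% | 18.6% |
| .7 | 2.4 | 0.645 | 35.5% | 20.6% |
| .8 | 2.6 | 0.620 | 38.0% | 22.4% |

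**Fewer visits**, rho .5 to .8

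- m = 2.5: DEFF 1.75 to 2.2; 24.4% to 32.6% too narrow; type I error 13.8% to 18.6%.
- m = 2: DEFF 1.5 to 1.8; 18.4% to 25.5% too narrow; type I error 11.0% to 14.4%.
- m = 1: DEFF 1; no shortfall.

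These lines put the mean number of visits into the formula as if everyone had the same number. With unequal counts, m should be the sum of squared counts over the sum of counts, which is larger. Suppose 80% attend Visit 2 and 80% of those attend Visit 3. The mean is 1 + .8 + .64 = 2.44, but the effective m is (.20×1 + .16×4 + .64×9)/2.44 = 6.6/2.44 = 2.70. At rho .7, DEFF = 1 + 1.70 × .7 = 2.19 and the interval is 32% too narrow. The figures by mean visits are therefore on the low side when dropout varies between people.

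**Simulation** (728 participants, 2,000 runs, no true effect)

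- Complete visits, rho .5, .6, .7, .8: naive/true SE 0.708, 0.672, 0.640, 0.617; type I error 16.6%, 19.6%, 21.7%, 22.4%.
- Dropout as above, rho .7: ratio 0.671; type I error 19.2%.
- Heavier dropout (60% at Visit 2, 70% of those at Visit 3), rho .7: ratio 0.697; type I error 16.8%.
- Participant-clustered standard errors in the same runs: type I error 4.9% to 5.4%.

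**Separate lm() at each visit.** This does not narrow any interval, but it gives three tests of one hypothesis with no designated visit. The chance of at least one false positive is 1 − .95³ = 14.3% if the tests were independent, and less when they are positively correlated.

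**The case against.** The strongest reply is that the SAP never says visits are stacked. The all-timepoints sentence describes the dataset, not the Aim 1 data frame, and Aim 2's future PCL-5 could by itself explain why follow-up visits are needed. The code is labelled as only similar to what will be run, and it carries no visit variable, which a person-by-visit file would normally have. Other parts of the SAP keep visits apart: the multiple-group factor analysis, the cross-lagged panels, the sleep mediation and the rumination analysis. If Aim 1 uses one visit per person, lm() is valid.

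All of that stands, and it rules out a stronger reading. A reader might infer that the Health LiTT interval will be about a third too narrow. The documents do not support that. With three complete visits, exactly one third needs rho = (1.5² − 1)/2 = .625, and no correlation is given anywhere; follow-up is also known to be incomplete. Nor do the figures carry over to Aim 3, whose PROMIS predictors are measured at each visit and vary within person. Their standard errors in a stacked lm() would also ignore clustering, but by an amount this formula does not give.

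The reply does not make the text adequate. As written, the stated data and the stated model together give an invalid interval. Each of the other readings, baseline only or separate models by visit, needs a sentence that is not there. Where other analyses in the SAP depend on the visit, such as the sleep mediation and the RRS factor analysis, the visit is named.

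**Conclusion.** The point holds as a conditional one. The PCL-5 section commits the project to all three visits, gives only lm() for Aims 1 and 3, and does not say which visit enters or how repeats are handled.

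If visits are stacked, the Aim 1 interval for Health LiTT is about 29% to 38% too narrow with three complete visits and an assumed rho of .5 to .8 (type I error about 17% to 22%). It is about 18% to 33% too narrow with 2 to 2.5 visits per person, or somewhat more if visit counts are uneven. If one visit per person is used, the shortfall is 0%. The stacking and the correlation are both assumptions, so no single figure should be quoted as the plan's error.

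This is a project added late to the SAP and does not touch the primary DIF analyses. It does bear on this project's main coefficient, and it should be settled before the analysis is run.

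**What to change.** For Aims 1 and 3, choose one route and write it into the SAP:

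- State that lm() uses baseline PCL-5 only, and limit the all-timepoints sentence to the aims that use later visits; or
- To use all visits, fit a linear mixed model with a participant random intercept and visit as a factor, or keep the regression, add visit, and cluster standard errors by participant.

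The correlations that screen PROMIS domains in Aim 3 need the same choice of visit.

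For Aim 2, name the follow-up visit that supplies the future PCL-5. If visits are pooled, resample participants rather than rows in the bootstrap.

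The cost is a few sentences in the SAP, one line of code and no new data. The interval may be wider than the one a stacked lm() would report.

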# The model will have a form similar to the R code below:  
# Note: race and ethnicity will be analyzed in English-speaking participants  
model <- lm(posttraumatic_stress ~ Health_LiTT + education + age + gender + race, data = data)  
summary(model)
```

The results will be evaluated by examining the magnitude and 95% confidence intervals for health literacy, as measured by Health LiTT. We will use “non-Hispanic white” as the reference category, and all other categories will be binary coded (0/1).

For Aim 1, the statistical analysis will involve a multiple linear regression model to explore how various factors such as health literacy (as measured by the Health LiTT test) and demographics such as education, age, gender, race, and ethnicity predict levels of posttraumatic stress (as per the PCL-5). The linear regression model will estimate the relationships between these variables. This will also include the calculation of coefficient estimates, confidence intervals, and significance levels. We will also explore assumptions of linear regression such as linearity, homoscedasticity, normality of residuals, and multicollinearity. We will assess all these aspects to ensure that there is no individual data point that disproportionately impacts results. For ethnicity, “non-Hispanic white” will serve as the reference group, and other ethnic categories will be binary coded (0/1; 0 for not belonging to this category and 1 for belonging to it). The results will be evaluated by examining the magnitude and 95% confidence intervals for health literacy, as measured by Health LiTT. We will also evaluate model goodness-of-fit (via R-squared statistic) to understand more about how well the model explains any variability in posttraumatic stress. We may explore interaction terms and model comparison as needed.

Aim 2 example code:

```
# Example mediation analyses will be conducted using lavaan  
library(lavaan)
```

Define the model with “c” pathways being direct effects:

```
model <- '  
PCL5 ~ c1 * education + c2 * age + c3 * gender + c4 * race  
Health_LiTT ~ a1 * education + a2 * age + a3 * gender + a4 * race  
PCL5 ~ b * Health_LiTT
```

Indirect effects (mediation):

indirect := a * b'

We will evaluate the statistical significance of indirect effects using 95% bootstrapped confidence intervals.

For Aim 2, we will conduct mediation analysis to explore whether health literacy mediates the relationship between baseline demographic factors (education, age, language, gender, race and ethnicity) and future stress-related symptoms as measured by the PCL-5. We will run separate models for English-speaking and Spanish-speaking participants to assess language-based differences in mediation. We will carry out mediation analysis using the lavaan package in R. This model will be defined with direct effects, in this case, the "c" pathways to represent the relationships between demographic variables and posttraumatic stress-related symptoms. Health literacy will be displayed as an intermediate variable between demographic factors and posttraumatic stress-related symptoms. The "a" pathways demonstrate the effect of demographics on Health Literacy, and the "b" pathways demonstrate the impact of health literacy on posttraumatic stress-related symptoms. Their indirect effects (mediation) will be estimated by the product of the "a" and "b" pathways (a*b). To evaluate the statistical significance of these indirect effects, we will use bootstrapped confidence intervals. Specifically, we will focus on the 95% confidence intervals to determine whether health literacy indeed acts as a significant mediator. If the confidence interval does not include zero, then this will suggest a statistically significant mediation effect.

Aim 3 description:

Aim 3 will rely on the lm() function or R for linear models as well as correlational analyses.

For Aim 3, we will conduct analysis that aims to identify which aspects of health-related quality of life (as measured by the PROMIS-57 Profile v2.1) are associated with posttraumatic stress-related symptoms (as measured by the PCL-5). The PROMIS-57 includes domains such as Physical Function, Anxiety, Depression, Fatigue, Sleep Disturbance, Ability to Participate in Social Roles and Activities, Pain interference, and Pain Intensity. We will examine the relationship between these quality-of-life domains and trauma symptoms while statistically controlling for demographic variables and health literacy. For this analysis, we will begin with assessing the correlations (using the psych package in R) between the PROMIS-57 domains and PCL-5, in the overall sample and also stratified by language. This may identify any significant relationships between quality of life domains and posttraumatic stress symptoms. Domains that suggest association with posttraumatic stress symptoms will be entered into a regression model with demographics included as covariates (to control for potential influence) and further evaluate the distinctive influence of quality of life domains predicting trauma symptoms. Lastly, language will be used as a moderator in the regression model to assess whether these relationships differ by language.

Effect size

I am focusing on unstandardized regression coefficients. In some cases, I may inspect standardized regression coefficients.

Inference criteria

Any regression coefficients with a 95% CI not containing zero will be regarded as significant.

Assumption Violation/ Model Non-Convergence

We will inspect the distribution of residuals for each model. If residuals suggest a departure from normality, robust regression and/or bootstrapping will be considered. If a model does not converge, we will explore other estimators in lavaan or modifications to the model, such as dropping covariates that are not needed.

Exploratory analysis

For research questions 1 and 3, language will be explored as a moderator. For research question 2, we will explore separate models for English and Spanish.

REFERENCES CITED

1. Affairs HlrotCoS. Ad Hoc Committee on Health Literacy for the Council on Scientific Affairs, American Medical Association. *JAMA*. 1999;281(6):552-7.

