Using a large sample, we will determine the psychometric properties of health questionnaires across levels of health literacy. Testing will be conducted in English and Spanish, across two modes of administration (paper-and-pencil vs. talking touchscreen). Each participant will have three visits (baseline, 3-month, and 6-month follow-up), described below, in order to determine changes in psychometric properties over time. We will use *differential item functioning* (DIF) and other psychometric analyses to identify questionnaire items with varying characteristics across levels of health literacy. Before the COVID-19 pandemic, our original plan was to recruit $N = 1216$ participants for in-person assessments. At the time of this plan our final N is 728 participants who have completed a health literacy assessment; some of these participants are missing data on subsequent questionnaires. In-person recruitment was put on hold during the COVID-19 pandemic; in order to adapt the the pandemic, a subset of participants ($N = 304$) was invited to a phone-based protocol that included data collection about the impact of COVID-19, vaccine confidence, and health-related quality-of-life (PROMIS-29 profile).

- **Develop alternative modes of test administration that can better accommodate people with low health literacy.** National statistics indicate that 14% of adults in the United States have below basic reading skills, and over 75 million Americans have below basic or basic health literacy skills.¹⁴ These data strongly indicate that many individuals seeking health care will have difficulties with written questionnaires, even those that have been carefully developed such as those in the NIH PROMIS. We will test an alternative mode of administration that has been specifically designed to aid people of low health literacy – a computer-assisted “talking” version that uses speech technology that participants can privately access as needed to have items and response options

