$$\text{item slope}_j = a_j + b1_j * \text{Health LiTT} + b2_j * \text{Administration Type} + b3_j * \text{Interaction}$$

where j is an index for the k items (8 items in this case).

We will use Mplus in conjunction with the aMNLFA²⁴ package of R. Following the MNLFA procedure outlined by Curran et al.,²⁵ we will test models allowing item parameters (intercept and slope) to vary as a function of hypothesized DIF variable, one item at a time, in order to arrive at a final model. We will use the final model to generate item characteristics curves (ICCs, which will show the estimated probabilities of endorsement for each item across different levels of meaning and purpose. Among non-invariant items, we will consider differences (due to DIF variables) in probability endorsement of 10% to be potentially meaningful scientifically. Using the final model, we will also plot meaning and purpose factor scores by healthy literacy and administration type to understand the relationship among these variables. For these analyses, we will use all available baseline data collected through March of 2020 ($N = 566$ English speakers).

Longitudinal analyses of Meaning and Purpose Predicting Quality of Life. In addition to examining DIF by health literacy in the NIH Toolbox Meaning and Purpose measure (as described above), cross-lagged panel analyses will be used to examine whether meaning and purpose predicts health-related quality of life (i.e., anxiety, depression, fatigue, pain intensity and interference, physical function, sleep disturbance, and disruption of social roles and activities) over time across the three study assessments. We will also identify covariates including sociodemographics associated with meaning and purpose (i.e., age, gender, financial strain, education, race/ethnicity, language). We hypothesize that greater meaning and purpose will prospectively predict greater quality of life at subsequent study assessments. We will only include participants who could have provided complete data before we ceased recruitment due to COVID-19. Thus, we will exclude participants who are 1) were enrolled on or after 16 September 2020, and 3) missing their 6-month assessment. In this way, data will not be systemically missing due to censoring from the COVID-19 pandemic (i.e., to be eligible, the person would have had sufficient time to complete all three assessments before the COVID-19 pandemic).

Exit Interview

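### PCL-5 Aim 2 sets out to assess language differences in mediation but specifies no comparison of the English and Spanish indirect effects

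*SAP*

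**What the plan says.** The analysis is in the SAP section on health literacy as a possible mediator between demographics and stress and trauma symptoms, added for Version 5.1. That section falls under the heading for other interim and exploratory analyses.

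- **Aim 2, list of aims:** "Will run separate models for English and Spanish".
- **Aim 2, Analysis Plan:** this gives the separate models a comparative purpose: "We will run separate models for English-speaking and Spanish-speaking participants to assess language-based differences in mediation".
- **Inference rule:** "We will evaluate the statistical significance of indirect effects using 95% bootstrapped confidence intervals", and then "If the confidence interval does not include zero, then this will suggest a statistically significant mediation effect". Both statements apply within a single model.
- **Exploratory analysis paragraph:** "For research question 2, we will explore separate models for English and Spanish". For questions 1 and 3 the same paragraph treats language as a moderator.
- **Predictors:** the Aim 2 prose lists "baseline demographic factors (education, age, language, gender, race and ethnicity". The example lavaan code has education, age, gender and race, and no language term.

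Aim 2 has no multi-group model, equality constraint, language interaction or interval for a difference in indirect effects. The allowance for interaction terms and model comparison closes the Aim 1 text and does not extend to Aim 2.

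**The concern.** The separate models are meant to show whether mediation differs by language, but each one answers only whether mediation is detectable in that language. Two within-group tests can disagree when the two effects are the same, because detection depends on sample size as well as on effect size. If the report goes by the stated rule, a reader could conclude that literacy mediates in English speakers and not in Spanish speakers when the data do not show a difference. In a bilingual health-literacy study that would be a substantive conclusion, and it would fall on what appears to be the smaller group.

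The predictor list adds a smaller fault. Language is constant within a language-specific model, so its path cannot be estimated there.

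**Working it through.** **No figure to reproduce.** The SAP gives no sample size, power or path size for this aim, so the check asks how often the stated rule gives discordant answers when mediation is identical in both languages.

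**Group sizes.**
- SAP Study Objectives: "At the time of this plan our final N is 728 participants who have completed a health literacy assessment".
- SAP Meaning and Purpose DIF analysis: "we will use all available baseline data collected through March of 2020", with 566 English speakers.
- If the 566 are a subset of the 728 (an assumption), Spanish speakers number at most 728 − 566 = 162 at baseline. The ratio is 566/162 = 3.5, and the Spanish standard error is about √3.49 = 1.87 times the English one.
- The planned split was 1:1 (304 English and 304 Spanish speakers per site, SAP Table 2).
- The outcome is future PCL-5. Follow-up completers per language are not stated.

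**Closed-form approximation.** Take standardised paths a and b (assumed) and call the indirect effect significant when both paths are:
- z_a = a√n / √(1 − a²)
- z_b = b√[n(1 − a²)] / √(1 − b²)
- power ≈ Φ(z_a − 1.96) × Φ(z_b − 1.96)

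For a = .30 and b = .15:
- English, n = 566: z_a = 7.48, z_b = 3.44; power = 1.000 × .931 = .931.
- Spanish, n = 162: z_a = 4.00, z_b = 1.84; power = .979 × .453 = .444.
- English only: .931 × (1 − .444) = .518. Spanish only: .444 × (1 − .931) = .031. Total disagreement is about .55.
- Equal groups, n = 364 each: power .788; disagreement 2 × .788 × .212 = .334.

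Over a = .20 to .30 and b = .10 to .20, the English-only probability runs from .996 × (1 − .684) = .315 (a = .30, b = .20) to .941 × (1 − .349) = .61 (a = .20, b = .15). Simulation of the same rule gives 32.5 to 62.5%. At a = b = .30 the closed form gives 1.000 × (1 − .949) = 5%, and simulation gives 6%.

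**Percentile-bootstrap simulation.** Identical paths in both languages, direct effect 0.1, 600 draws per group, 1500 replications. Entries are % of runs; the first four result columns and the last are for 566 v 162.

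| a, b | English sig. | Spanish sig. | Disagree | English only | Disagree, 364 v 364 | Interval for difference excludes 0 |
|---|---|---|---|---|---|---|
| 0, 0 | 0.2 | 0.3 | 0.5 | 0.2 | 0.7 | 0.3 |
| .14, .14 | 83.1 | 16.9 | 72.6 | 69.4 | 48.9 | 5.3 |
| .20, .20 | 99.3 | 49.4 | 50.7 | 50.3 | 11.6 | 4.7 |
| .26, .26 | 100 | 81.6 | 18.4 | 18.4 | 0.7 | 5.1 |
| .39, .14 | 87.7 | 40.9 | 57.7 | 52.3 | 41.8 | 6.1 |
| .39, .39 | 100 | 99.9 | 0.1 | 0.1 | 0.0 | 4.7 |

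With an assumed 30% attrition (396 v 113), disagreement in the five non-null rows is 58.5, 69.1, 36.8, 61.1 and 2.3%. The interval for the difference excludes zero in 3.9 to 7.3%.

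**Power of the direct contrast.** At 566 v 162 with a = .30 in both languages, b = .15 in English and b = 0 in Spanish, two simulations put power at about 32% and 36%. With English b = .20 it is about 50%.

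**The case against.** The strongest reply is that the SAP never says discordant significance will be called a language difference. The zero-exclusion rule decides whether literacy mediates within a model. The effect-size paragraph emphasises unstandardised coefficients, so a descriptive comparison of two estimates and their intervals would fit the text. The work is also labelled exploratory, and Hypothesis 2 predicts mediation without predicting that it differs by language. All of this stands. It lowers the priority and makes the concern one of risk. It does not supply a criterion for the stated purpose of assessing differences, and an exploratory label does not turn two within-group tests into a comparison.

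A reader might infer three stronger points that the documents do not support:

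- **That unequal sample size is the whole cause.** At a = b = .14, equal groups still disagree in 48.9% of runs, against 72.6% at 566 v 162. Imbalance enlarges the disagreement and tilts it towards English-only.
- **That the analysed Spanish group is at least 3.5 times smaller.** The 566 and the 728 come from different sections and perhaps different cut-off dates. Their difference bounds baseline numbers only if one set contains the other, and follow-up numbers by language are not given.
- **That Aims 1 and 3 already have a firm language test.** There too the SAP's exploratory paragraph describes language only as a moderator to be explored.

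The predictor-list fault is confined to one phrase in the prose, since the code and Hypothesis 2 already leave language out.

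**Conclusion.** The concern holds as a gap in an exploratory analysis: Aim 2 has a comparative purpose and no comparative quantity. The roughly 32 to 62% chance of English-only significance under identical mediation depends on the assumed 566 v 162 split, the assumed path sizes, and a report that goes by the within-model rule. Outside that range of paths the problem can be small, as the results for a = b = .30, for null effects and for very large effects show. An interval for the difference keeps false claims near 5% for non-zero effects under either split, so it is the better method. Its limited power means that it guards against false differences and cannot establish equal mediation. The change is worth making before the analysis is run, but no confirmatory claim of the study depends on it.

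**What to change.** 1. Fit one two-group lavaan model with language as the grouping variable, language-specific a and b paths, and the same covariate set in both groups.
2. Define each predictor's indirect effect in each language and its English-minus-Spanish difference, and bootstrap the difference. The example code labels paths a1 to a4 but builds a single indirect effect from an unindexed a, so these products have to be written out in any case.
3. Claim a language difference only if the 95% interval for that difference excludes zero.
4. Report n per language, and state that a non-significant difference is not evidence of equal mediation because power is limited.
5. The Aim 1 code comment says race and ethnicity will be analysed in English speakers. If an English-only model with race and ethnicity is wanted for Aim 2, report it separately and keep it out of the contrast. Otherwise the difference would mix language with adjustment set.
6. Delete language from the Aim 2 predictor list in the prose.

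The cost is a few lines of code and SAP wording, with no new data. The drawback is that the interval for the difference is likely to be wide.
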